The actual number of subjects enrolled in the Induction Phase will be driven by observed induction failure rates and will be such to allow for approximately 466 subjects to be randomized in the Maintenance Phase. Subjects enrolled in the Induction Phase will receive induction chemotherapy comprised of oxaliplatin and either 5-fluorouracil (5-FU) or capecitabine (Induction Phase) for 12 weeks. Following the Induction Phase, subjects who experience a complete response (CR), partial response (PR), or stable disease (SD) will enter the Maintenance Phase and be randomly assigned to receive either avelumab, or continuation of the same chemotherapy regimen from the Induction Phase (Maintenance Phase).

The dose and schedule of the chemotherapy during the Induction Phase are as follows or in accordance to the label instructions and per local guidelines:

- Oxaliplatin at 85 mg/m² intravenous (IV) on Day 1 with leucovorin 200 mg/m² IV on Day 1 (or equivalent levoleucovorin dose) followed by 5-FU at 2600 mg/m² IV continuous infusion over 24 hours on Day 1, given every 2 weeks (for up to 12 weeks)
- OR
- Oxaliplatin at 85 mg/m² IV on Day 1 with leucovorin 400 mg/m² IV on Day 1 (or equivalent levoleucovorin dose) followed by 5-FU at 400 mg/m² IV push on Day 1 and 2400 mg/m² IV continuous infusion over 46-48 hours (Days 1 and 2) given every 2 weeks (for up to 12 weeks)
- OR
- Oxaliplatin at 130 mg/m² IV on Day 1 with capecitabine at 1000 mg/m², twice daily for 2 weeks followed by a 1-week rest period given every 3 weeks (for up to 12 weeks).

Local label and guidelines should be followed for specific starting doses due to renal or hepatic impairments and for subsequent dose modifications due to different toxicities.

Upon completion of chemotherapy in the Induction Phase, subjects without disease progression (subjects with SD, PR, or CR) will be eligible for randomization to the Maintenance Phase where they will receive either avelumab, or continue the same regimen of chemotherapy from the Induction Phase.

Treatment during the Maintenance Phase are as follows:

1. For subjects randomly assigned to avelumab: avelumab will be given at a dose of 10 mg/kg as a 1-hour IV infusion once every 2 weeks until disease progression
2. For subjects randomly assigned to chemotherapy: the same regimen of oxaliplatin-fluoropyrimidine doublet as in the Induction Phase will be continued until disease progression.

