5.1.1 Overall Design

Approximately 466 subjects are planned to be enrolled in the Maintenance Phase. The actual number of subjects enrolled in the Induction Phase will be driven by observed induction failure rates and will be such to allow for approximately 466 patients to be randomized in the Maintenance Phase. At the time of this protocol amendment, subject enrollment in the Maintenance Phase is complete, with 499 subjects randomized into the Maintenance Phase. Subjects enrolled in the Induction Phase will receive a first-line therapy comprised of oxaliplatin and either 5-FU or capecitabine (Induction Phase) for 12 weeks (see Section 5.1.2.1).

Following the Induction Phase, subjects who experience a CR, PR, or SD after 12 weeks (approximately 466 subjects) will be randomly assigned (Maintenance Phase) to receive either avelumab (see Section 5.1.2.2.1) or continuation of the same regimen of chemotherapy from the Induction Phase (see Section 5.1.2.2.2). Subjects who are not deemed eligible to receive further chemotherapy will receive best supportive care (BSC) alone with no active therapy.

Prior to randomization, Investigators must specify which of treatments (continuation of the same regimen of chemotherapy from the Induction Phase versus BSC) will be selected for subjects in chemotherapy control arm.

CCI

After the Induction Phase, all subjects will be evaluated for eligibility into the Maintenance Phase by an independent radiologist using RECIST v1.1.

Study treatment will continue until:

- Disease progression (see Section 5.5.1)
- Significant clinical deterioration (clinical progression) by Investigator's opinion
- Unacceptable toxicity per Investigator opinion, or
- Any criterion for withdrawal from the trial or trial treatment is fulfilled (see Section 5.5).

Subjects receiving avelumab may continue treatment past the initial determination of disease progression per RECIST v1.1 as long the following criteria are met:

- Investigator-assessed clinical benefit, without any rapid disease progression
- Tolerance of trial treatment
- Stable Eastern Cooperative Oncology Group (ECOG) performance status (PS) (PS = 0 or 1)
- Treatment beyond progression will not delay an imminent intervention to prevent serious complications of disease progression (for example, central nervous system metastases).

The decision to continue avelumab treatment beyond progression should be discussed with the Medical Monitor and documented in the study records.

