Subjects receiving maintenance chemotherapy will receive trial treatment until PD per RECIST version 1.1, for the accepted maximal duration of the agent(s) selected, significant clinical deterioration (clinical progression), unacceptable toxicity, withdrawal of consent, or if any criterion for withdrawal from the trial or trial treatment is fulfilled.

On-study subject management and study endpoint evaluation will be based on Investigator assessments (see Section 7.3).

[figure not shown]
Subjects will attend clinic visits at regular intervals to receive trial treatment and for efficacy and safety assessments (see Section 7.1).

The primary endpoint of the trial is OS, defined as the time (in months) from randomization to the date of death, regardless of the actual cause of the subject's death. The primary endpoint OS will be tested in all randomized subjects (intent-to-treat [ITT] Analysis Set) and in PD-L1+ subjects (PD-L1+ Analysis Set). The PD-L1 expression status will be determined according to the conventional tumor-cell (cell number-based percentage) scoring method where subjects with PD-L1 tumor expression $\geq 1\%$ are considered to be PD-L1+.

Safety endpoints include AEs, assessed throughout the trial and evaluated using the NCI-CTCAE v4.03; physical examinations; clinical laboratory assessments; concomitant medications; vital signs; electrocardiogram (ECG) parameters; and ECOG PS.

The trial design schematic is presented in Figure 1.

Figure 1 Schematic of Trial Design

All subjects in both arms will receive BSC as background therapy as specified in Section 6.1.4. BSC=best supportive care; 5-FU=5-fluorouracil; n=number of subjects; PD=progressive disease.

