5.1.2.2.2 Chemotherapy Arm

Subjects randomly assigned to the maintenance chemotherapy arm will receive first-line chemotherapy according to the dosing schedule (see Section 6.2 and Table 3 to Table 4) or in accordance to the label instructions and per local guidelines) until disease progression, unacceptable toxicity, for the accepted maximal duration of the agent(s) selected, or any of the criteria for withdrawal from trial treatment is fulfilled (Section 5.5).

The dose and schedule during the Maintenance Phase are as follows:

Subjects randomly assigned to chemotherapy will continue the same regimen of oxaliplatin-fluoropyrimidine doublet as they received during the Induction Phase until disease progression.

- Subjects who are not deemed eligible to receive further chemotherapy will receive BSC alone with no active therapy. Prior to randomization, Investigators must specify BSC treatment for these subjects (see Table 5)
- For subjects receiving chemotherapy (oxaliplatin + 5-FU or oxaliplatin + capecitabine), dose modifications after the starting dose are allowed if the continuation of the oxaliplatin-fluoropyrimidine doublet, or a component thereof, is prohibited by toxicity. For subjects intolerant to further oxaliplatin, single-agent capecitabine or 5-FU + leucovorin will be an option for dose modification.

Additionally, in order to reduce the incidence and severity of nausea and vomiting as well as the severity of hypersensitivity reactions, subjects will be administered pretreatment prior to each therapy infusion per local institutional practice.

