5.2.3 Rationale for Switching Subjects from Chemotherapy to Avelumab

The proposal to switch subjects assigned to the experimental arm after they have completed 12 weeks of chemotherapy is appropriate for the following reasons:

- There is no data supporting that additional chemotherapy beyond 4 to 6 cycles (up to 12 weeks of treatment) will result in improved survival in the context of a disease where it is common practice to re-induce patients at the time of disease progression. Patients who have not responded to or who will cease to respond to avelumab will be re-induced either with platinum-based doublets or with drugs that have shown clinical benefit as a second-line therapy. Subjects will be monitored every 6 weeks and rescue therapy may be administered once disease progression is established.
- Treatment of patients with avelumab has resulted in an ORR of 15% in patients with gastric cancer from Asian and non-Asian regions. Some of these responses were long lasting and a number of subjects with prolonged SD were also observed. Based on these data, it is reasonable to interrupt chemotherapy after 12 weeks to initiate an immunotherapy that has been reported to induce prolonged responses in advanced gastric cancer patients who will ultimately progress after initial chemotherapy regimens.
- For subjects randomly assigned to receive additional chemotherapy in the Maintenance Phase, it is recommended that the chemotherapy regimen does not to exceed 6 cycles. This is supported by the previously established regimen in the registration study for trastuzumab (TOGA). In conclusion, switching subjects after 12 weeks of chemotherapy to receive avelumab treatment is considered appropriate.

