In case a subject with a confirmed CR relapses after stopping treatment, but prior to the end of the trial, 1 re-initiation of treatment is allowed at the discretion of the Investigator and after agreement with the Medical Monitor. In order to be eligible for retreatment, the subject must not have experienced any toxicity that led to treatment discontinuation of the initial avelumab therapy. Subjects who re-initiate treatment will stay on trial and will be treated and monitored according to the protocol.

Maintenance Chemotherapy Arm:

Maintenance chemotherapy will continue until disease progression or unacceptable toxicity or until the maximum acceptable dosing is achieved at the discretion of the Investigator.

Subjects who are not deemed eligible to receive further chemotherapy will receive BSC alone with no active therapy until disease progression. Prior to randomization, Investigators must specify BSC treatment for these subjects.

iv) The Follow-up Phase will include a post-treatment period and long-term follow-up visits. During the post-treatment period (from treatment discontinuation to Safety Follow-up), a Safety Follow-up visit will be scheduled 30 days after last treatment and a phone call will occur 90 days after treatment discontinuation.

A long-term follow-up visit will occur every 12 weeks for 5 years after the last subject receives the last dose of study drug (see Section 7.1.7 for details).

During Screening, induction, maintenance and post-treatment periods, subject will undergo visits and assessment procedures as per described in the Schedule of Assessments (Table 1 to Table 7).

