If there are multiple complete assessments for any scheduled visit during the treatment phase, the assessment that is closest to the planned visit per protocol will be used in the analysis. If there are multiple complete assessments at Discontinuation visit and End of Treatment visit, the first assessment will be used in the analysis.

- Longitudinal analysis of change from Maintenance Phase baseline

A mixed-effects model repeated measures (MMRM) analysis will evaluate longitudinal change from baseline on the QLQ-C30 physical function scale and the QLQ-STO22 symptom scales. Covariates will include the Maintenance Phase baseline score for the domain score being evaluated and the randomization stratification factor. The questionnaire completion time point (Maintenance Phase-study day), including both scheduled and unscheduled visits, will be analyzed as a continuous variable. The overall significance of the difference between the MMRM trajectories for the treatment arms will be tested. An unstructured covariance structure will be used, if possible, though a simpler covariance structure will be used if the model does not converge.

- Subject level change from Maintenance Phase baseline

For the HRQoL domain scores analyzed using MMRM, an empirical cumulative distribution function (eCDF) curves, separated by treatment arm, will display the proportion of subjects who experienced specific changes from Maintenance Phase baseline to end of treatment. For each eCDF, the range of change scores will be displayed on the x-axis, and the cumulative percentage of patients achieving that change score or better will be displayed on the y-axis. The eCDF may be interpreted by choosing a change score magnitude that may be considered clinically meaningful on the x-axis and comparing the rate of subjects who achieved at least that amount of change (on the y-axis) between the treatment arms.

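### The quality-of-life eCDF compares the arms at end of treatment, a time set by arm-specific stopping rules, so part of any difference may reflect when and why treatment stopped

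*SAP*

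**What the plan says.** SAP 15.2.3, in the paragraph on subject-level change, plans eCDF curves by arm for the domains analysed by MMRM. The curves "will display the proportion of subjects who experienced specific changes from Maintenance Phase baseline to end of treatment". The reader is told to choose a meaningful change score and read the curves by "comparing the rate of subjects who achieved at least that amount of change (on the y-axis) between the treatment arms". The section sets no week for this change. It also gives no rule for a subject without an end-of-treatment questionnaire, and it does not impute scores.

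Protocol 7.1.5 ties the End-of-Treatment visit to the decision to stop, within 7 days of it, and the stopping rules differ by arm:

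- **Control chemotherapy.** Protocol 5.1.2.2.2 allows treatment "for the accepted maximal duration of the agent(s) selected" as one of the end points, alongside progression and toxicity. Sections 5.1.1, 5.2.6, 6.2.2 and 7.1.4 have a similar provision. In 5.2.3, "it is recommended that the chemotherapy regimen does not to exceed 6 cycles".
- **Control, BSC only.** These subjects "will receive BSC alone with no active therapy until disease progression" (Protocol 5.2.6).
- **Avelumab.** Treatment runs to progression or toxicity, and "Subjects receiving avelumab may continue treatment past the initial determination of disease progression per RECIST v1.1" if stated criteria are met (Protocol 5.1.1).

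The protocol is not consistent about control. The synopsis methodology says that "the same regimen of oxaliplatin-fluoropyrimidine doublet as in the Induction Phase will be continued until disease progression", and its list of stopping reasons for the chemotherapy arm names no maximal duration. SAP Section 5 repeats that version.

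**The concern.** A responder-type comparison is fair when both arms are scored at the same time, or when the time is unrelated to arm. Here the scoring time is the stopping time. A control subject who stops at the maximal duration is scored while progression-free. A comparable avelumab subject continues and may be scored at or after progression, when quality of life is likely to be worse. The curves could then separate even if the drugs had identical effects on quality of life, and a reader following the SAP's guidance would credit the difference to treatment.

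**Working it through.** The plan gives no figure for the eCDF, so there is nothing of its own to reproduce. The check covers how different the stopping times could be, what that could do to the curves, and how many subjects lack a score.

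**1. Control stops before progression.** Six cycles last about 12 weeks (2-weekly) or 18 weeks (3-weekly), that is 84/30.4375 = 2.76 or 126/30.4375 = 4.14 months. Median PFS is not in the documents; 3, 4.5 and 6 months are assumed. With exponential times, the share progression-free at time t is exp(−ln2 × t / median):

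| Assumed median PFS | Week 12 | Week 18 |
|---|---|---|
| 3 months | 53% | 38% |
| 4.5 months | 65% | 53% |
| 6 months | 73% | 62% |

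If the 6-cycle recommendation is followed, many control end-of-treatment scores could precede progression. If it is not, far fewer would.

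**2. Effect on the curves with no treatment effect.** Illustrative inputs, none from the documents, for a scale where higher is better: change-score SD 20, mean change −2 without progression and −12 (or −10) at progression, and a threshold of 10 points worsening.

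- Without progression: Φ((−10 + 2)/20) = Φ(−0.4) = 0.345.
- At progression: Φ((−10 + 12)/20) = Φ(0.1) = 0.540, or Φ(0) = 0.500 with the smaller drop.
- Difference in proportion worsening: 0.195 with a 10-point drop, 0.155 with an 8-point drop.

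The spurious gap is (control share of non-PD stops − avelumab share) × that difference. For 40% against 10%, control has 0.6 × 0.540 + 0.4 × 0.345 = 46.2% worsening and avelumab 0.9 × 0.540 + 0.1 × 0.345 = 52.0%, a gap of about 6 points.

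| Control non-PD stops | Avelumab non-PD stops | Gap, 8-point drop | Gap, 10-point drop |
|---|---|---|---|
| equal | equal | 0 | 0 |
| 30% | 20% | 1.6 | 2.0 |
| 30% | 10% | 3.1 | 3.9 |
| 40% | 10% | 4.7 | 5.9 |
| 50% | 10% | 6.2 | 7.8 |

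Each 10 percentage points of difference in non-PD stops moves the curves apart by 1.6 to 2.0 points. If avelumab had more such stops, the sign would reverse.

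**3. Subjects with no end-of-treatment score.** SAP Section 10 excludes data after the cut-off, and SAP 11.1 foresees subjects still on treatment. With 18 months of uniform accrual and 18 months of further follow-up (Protocol 8.1), the share still on treatment is (e^(−18λ) − e^(−36λ))/(18λ), with λ = ln2/median. For assumed median treatment durations of 3, 4.5, 6 and 9 months this gives 0.4%, 2.1%, 5.3% and 13.5%. The ceiling is the share still alive under the design medians: 29.6% on avelumab (15 months) and 17.8% on control (10.5 months). Subjects who die or miss the questionnaire add to the number without a score.

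**4. Which fixed times are available.** Tables 3 to 6 schedule questionnaires at Week 7 (Day 43) and Week 13 (Day 85) in every regimen. In Table 4, however, Week 13 is the seventh 2-weekly visit. A 5-FU control subject stopping after six cycles has a last dose at about Day 71, hence an End-of-Treatment score and a 30-day score at about Day 101 (± 5), but no scheduled Week 13 visit.

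**The case against.** The contrast is a partial difference in mix. Control subjects also stop at progression, and those on BSC only run to progression. Avelumab subjects also stop without progression: Protocol 5.1.3.2 requires discontinuation for most Grade 3 and 4 drug reactions, and 5.1.1 sets only a minimum of 12 months after a CR. Treatment past progression is optional. This stands. A reader might infer that the curves compare different disease stages by design, or that a bias of 3 to 8 points against avelumab is established. The documents support neither. The 3-to-8 figure needs avelumab non-PD stops held at 10%, for which there is no source.

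A reader might also infer that the plan discards the longest responders. The SAP does not say so. It is silent on subjects without an end-of-treatment score, and the numbers above suggest that few would still be on treatment.

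Time-aligned analyses already exist: by-visit summaries, line plots, and an MMRM on study day for the same domains. The eCDF carries no test and no multiplicity control. With about 200 scored subjects per arm (assumed), the standard error of a difference in proportions near 50% is √(2 × 0.25/200) = 5 points, as large as most of the gaps shown. All this lowers the weight. It does not change what the eCDF displays, or the SAP's suggestion to compare arms on it.

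**Conclusion.** The point holds at low weight. As written, the eCDF compares the arms at times that depend on arm-specific stopping rules, so part of any separation can reflect when and why treatment ended. The size cannot be determined from the documents. Under the illustrative score assumptions it is near 0 to about 8 percentage points for differences of 0 to 40 percentage points in non-PD stops, and it scales in proportion beyond that. How far the arms differ depends largely on which control-duration text was followed, and those texts disagree. The unstated handling of missing end-of-treatment scores is a second, probably smaller, gap. No confirmatory conclusion is affected.

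**What to change.** 1. Draw the between-arm eCDF at fixed times since randomization: at Week 7, and at Week 13 with a study-day window that admits End-of-Treatment and Safety Follow-up questionnaires. Taking midpoints between the 6-weekly questionnaire visits, (43 + 85)/2 = 64 and (85 + 127)/2 = 106, a window of about Day 65 to Day 106 would take in both scores of a 5-FU subject whose last dose was near Day 71. Allow for treatment starting up to 4 days after randomization. Where several scores fall in the window, use the one closest to the planned day, as the SAP already does for scheduled visits. Filtering on the scheduled Week 13 visit alone would drop 5-FU control subjects who stop at six cycles.
2. Report by arm, at each time, the number alive without a score and the number who died.
3. Keep the end-of-treatment eCDF as description only, without the between-arm reading. Show time since randomization and reason for stopping by arm, and state how subjects without an end-of-treatment score are handled.
4. Reconcile the texts on control treatment duration: the synopsis methodology and SAP Section 5 against Protocol 5.1.1, 5.1.2.2.2, 5.2.3, 6.2.2 and 7.1.4.

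The cost is a few SAP sentences, a window rule and one small table; the questionnaires are already collected. The downsides are that late changes do not appear in the fixed-time eCDF, the Week 13 window mixes on-treatment and off-treatment scores, and subjects with no score in the window, such as those who stopped well before it, remain missing.

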### **Missing Values and Imputation Rules**

If 50% or more of the items for a given scale are non-missing, then the Raw Score should be computed as the average of the non-missing items; if more than 50% of the items for a given scale are missing the scale score will be set to missing.

Missing data will be retained as observed, and no imputation of HRQoL scores will be conducted.

### 15.2.3.1 European Quality of Life (EuroQoL) - 5 Dimensions - 5 Levels (EQ-5D-5L)

The EQ-5D questionnaire is a generic measure of health status that provides a descriptive profile and a simple index value. It includes 5 items assessing mobility, self-care, usual activities, pain / discomfort, anxiety / depression on a 5-level response scale (EQ-5D-5L). It also includes a visual analogue scale ranging from 0 to 100 for self-rated health status. A higher score indicates better health status. Utilities can be derived from the EQ-5D, ranging from 0.0 (worst health state) to 1.0 (best health state).

The EQ-5D-5L scoring system will also be converted into a single index value. The index value is country specific and is a major feature of the EQ-5D instrument, facilitating the calculation of quality-adjusted life years (QALYs) that are used to inform economic evaluations of health care interventions. The Japan country-specific value set will be used in deriving the index value for Asian countries and ranges from -0.111 (worst health state) to 1.000 (best health state); the UK country-specific value set will be used in deriving the index value for non-Asian countries – it ranges from -0.594 (worst health state) to 1.000 (best health state).

